1.0 Objectives

The goal of this study will be to measure:

- 1) Total narcotic consumption
- 2) VAS pain scores
- 3) Length of stay in the post anesthesia care unit (PACU)

following total hip arthroscopy in two groups of patients, one that receives intra-articular (IA) morphine and clonidine in addition to the standard pre and postoperative analgesia and the other group that receives normal saline in addition to the standard pre and postoperative analgesics.

The primary goal of this study will be to determine if perioperative intra-articular morphine and clonidine injections will reduce the postoperative narcotic consumption, pain scores, and time to recovery for patients undergoing hip arthroscopy.

The primary outcome of this study will be narcotic consumption during PACU recovery duration, which will be measured by total opioid consumption in units of morphine equivalents. PACU opioid consumption will be calculated from the medications list, which is regularly recorded in the electronic medical record.

2.0 Background

Since January 2015 many of [name] patients have been receiving IA morphine and clonidine injections as prophylaxis for postoperative pain control after hip arthroscopy. However, prior to January 2015 IA morphine and clonidine were not administered as standard of care.

Because there is so little published about the efficacy of such injections in hip arthroscopy, the purpose of this study is to further explore this gap in knowledge.

A retrospective pilot study at Northwestern Memorial Hospital (under IRB STU00200639) has shown the proposed intervention to be successful in decreasing postoperative narcotic consumption. The control group receiving only the current standard of care had a 40 mEq narcotic consumption, while the interventional group receiving the additional IA morphine and clonidine had only a 23 mEq narcotic consumption ($p=.0259$).

Over the last few decades, the use and safety of arthroscopic hip surgery has considerably improved though the evolution and development of arthroscopic imaging and instrumentation¹. There is still a considerable amount of room for growth and research in comparison to arthroscopic knee and shoulder surgery, which have been around much longer. One area which needs attention is postoperative pain management for patients undergoing hip arthroscopy. The benefits to controlling postoperative pain are multifocal and range from improved patient comfort and decreased

Prospective Assessment of Perioperative Intra-Articular Morphine Injection in Hip Arthroscopy on Postoperative Pain Management

time of recovery to decreased narcotic consumption and reduced cost of care².

Many studies on the use of intra-articular morphine (IA) injections in arthroscopic knee surgery have demonstrated effectiveness in reducing both patient reported pain and narcotic consumption post-operatively³⁻⁵. Furthermore, studies have shown that intra-articular clonidine, an α_2 agonist, potentiates the analgesic effect of morphine when the two are used in combination⁶. While there is considerable evidence supporting the use of IA morphine for knee surgery, very little has been cited for such use in hip arthroscopy⁷. The purpose of our study is to expand upon the retrospective data that we have already analyzed to better assess the effectiveness of IA morphine and clonidine injections in reducing patient reported pain and narcotic consumption.

3.0 Inclusion and Exclusion Criteria

All patients who are undergoing a hip arthroscopy procedure by the senior surgeon ([name]) will be approached to participate in the study, with the exception of pregnant women, adults unable to consent, prisoners, and any patient under the age of 18 years.

Any patient with a medical contraindication to morphine or clonidine will not be included in either the therapeutic or control group. Additionally, for the final analysis, the data for all subjects in our data set will be analyzed using a random study number as the key identifier. In some cases, if there is substantial data missing for a subject, which would be otherwise essential for analysis, the subject's information for that particular analysis will be excluded. To the best extent possible, data that can be interpolated will be utilized.

4.0 Study-Wide Number of Subjects:

N/A

5.0 Study-Wide Recruitment Methods:

N/A

6.0 Multi-Site Research:

N/A

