8.0 Study Endpoints

The primary endpoint is patient narcotic consumption in the PACU after hip arthroscopy. Narcotic consumption will be measured by converting the patient's opioid consumption during their PACU recovery duration into morphine equivalents. This conversion is necessary to standardize different types of narcotics that can be administered in the PACU. We will also be determining the utility of IA morphine and clonidine in decreasing the patient reported pain in the PACU and during the first postoperative week, time until discharge from the PACU, and the quality of patient recovery using the QoR-15 survey.

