9.0 Procedures Involved

100 patients will be consented for this study. 50 for the "control group" injection and 50 for the "therapeutic group" injection. For patients who are consented and enrolled in this study, prior to surgery, [name] will place a written order to the OR pharmacy for the randomized injection. Each order placed will be associated with a sequential study number (1-100) to keep track of each patient and the intervention that they received. The OR pharmacy will randomize the injection into the control or therapeutic group, so as to keep the team involved in patient care blinded to the intervention.

In the preoperative holding area prior to surgery, all patients will be asked to fill out the QoR-15 questionnaire (see Appendix), rate their current level of pain on the Visual Analog Scale (0-10), and be asked if they have taken any pain medication in the past 24 hours. Those in the control group will receive a 11 mL injection of .9% normal saline, and the therapeutic group will receive a 11 mL injection of 10 mg morphine and 100 mcg of clonidine in .9% NaCl solution. Both injections will occur at the conclusion of the hip arthroscopy procedure. All other pre, peri, and postoperative procedures will follow the standard of care.

Postoperatively, pain scores, amount of narcotics used, and discharge times, which are recorded in the patient's medical record as part of standard of care, will be collected. The control group will be compared to the therapeutic group. All postoperative pain management will follow the normal standard of care procedures for hip arthroscopy patients.

Additionally, patients will be sent home with a short "diary" for logging their pain and narcotic consumption in the first week following surgery. They will be rating their pain and logging narcotic consumption at 6, 18, 24, 48 hours, and 7 days postoperatively. This diary will be collected from the patient at their two week follow-up appointment.

The research procedures required for this protocol include the intra-articular injection at the conclusion of the hip arthroscopy procedure. At

Prospective Assessment of Perioperative Intra-Articular Morphine Injection in Hip Arthroscopy on Postoperative Pain Management

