the conclusion of the hip arthroscopy, before closing the incision with sutures, an intra-articular injection of both morphine and clonidine, for the therapeutic group, or normal saline, for the control group, will be performed. All other operative procedures will occur as standard of care to ensure optimal patient safety.

- All standard of care procedures will take place for a hip arthroscopy procedure. No additional procedures are needed to reduce the magnitude of risk, as patients with a contraindication to morphine or clonidine will not be enrolled in the study, and patients will be under the watch of nurses, physician assistants, and doctors while in the postoperative recovery room.
- The only drugs used in this study that are beyond the standard of care for hip arthroscopy are intra-articular morphine and clonidine. In the context of this study, morphine and clonidine are FDA approved drugs for non-approved use. The control group will receive intra-articular normal saline, which is FDA approved.
- Northwestern's Powerchart electronic medical record system will be used to access patient medical records for those who consent to the study. Basic patient demographics, pre and post-op VAS pain scores, discharge times, and narcotic/analgesic consumption will be recorded from data in the medical records. The QoR-15 survey will also be used to assess patient quality of recovery. All data will be coded and stored in the attached Excel spreadsheet, which will be on a database in [name] locked office, only accessible to research personnel of the project via an encrypted password. All paper based documents will be kept in a locked cabinet in [name] office.

All data collected for this study can be found in the attached MS Excel spreadsheet and sample QoR-15 survey. Data points include age, sex, height, weight, tobacco use, VAS pain scores, discharge times, duration of surgery, discharge criteria score, medication use, and the following quality of recovery scores (as seen in the QoR-15): comfort, independence, and support. The postoperative diary will be asking patients for VAS pain scores, narcotic consumption, and potential complications at 6, 18, 24, 48 hours, and 7 days postoperative.

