23.0 Local Number of Subjects

100. 50 subjects in the therapeutic group. 50 subjects in the control group

24.0 Confidentiality:

N/A, single-center study

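### Preoperative opioid use is likely to predict PACU opioid consumption, but the plan neither specifies how to record it nor adjusts for it; the cost is precision, not bias

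*Combined protocol and SAP*

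**What the plan says.** **Who is eligible.** Section 3.0 (Inclusion and Exclusion Criteria) approaches "All patients who are undergoing a hip arthroscopy procedure by the senior surgeon", apart from pregnant women, adults unable to consent, prisoners and minors. The only exclusion tied to drugs is: "Any patient with a medical contraindication to morphine or clonidine will not be included in either the therapeutic or control group". Section 28.0 adds limits on language and cognition. Nothing restricts current or long-term opioid use.

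**What is measured.** Section 8.0: "The primary endpoint is patient narcotic consumption in the PACU after hip arthroscopy", converted to morphine equivalents.

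**What is recorded beforehand.** In the holding area patients will "be asked if they have taken any pain medication in the past 24 hours" (Section 9.0). As described, the question does not specify drug class, dose or duration of use. Section 9.0 also says that "narcotic/analgesic consumption will be recorded from data in the medical records", and its list of data points includes "duration of surgery, discharge criteria score, medication use". Neither chart item has a time window or names preoperative opioids.

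**Allocation and analysis.** Section 9.0: "The OR pharmacy will randomize the injection into the control or therapeutic group", with no strata described. Section 23.0 gives the numbers: "50 subjects in the therapeutic group. 50 subjects in the control group". Section 11.0 lists Student's t, Mann-Whitney and chi-square tests and names no baseline covariate.

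**The concern.** A patient who takes opioids regularly before surgery is likely to need more opioid in the PACU, so prior use bears directly on the quantity the trial compares. The plan could deal with it in three places: eligibility, allocation and analysis. It does so in none of them.

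The question described may not support a later repair either. If only a yes or no is kept, one acetaminophen tablet and a daily opioid give the same answer, and a regular user whose last dose was more than a day earlier answers no. Adjusting for that answer would not be adjusting for opioid use.

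Two things are at stake. Variation between users and non-users stays in the error term and lowers power. And if chance puts more users in one arm, the planned analysis does not correct the estimate for it.

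**Working it through.** **Inputs from the documents**
- 50 patients per arm (Sections 7.0, 9.0 and 23.0).
- Pilot consumption 40 mEq in controls and 23 mEq with the injection (Section 2.0), a difference of 40 − 23 = 17 mEq. The pilot SD and group sizes are not given.
- No alpha, power or SD is stated, so the sample size cannot be reproduced.

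**Assumptions (none is in the documents)**
- Share of regular opioid users *p*: 15%, range 10–25%.
- Extra PACU use by such patients *D*: 30 mEq, range 20–40.
- SD within users and within non-users: 30 mEq.
- Two-sided alpha 0.05.

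**Step 1. Chance imbalance.** The SD of the between-arm difference in user share is √(2*p*(1 − *p*)/50). Multiplying by 1.96 gives the 95% range, and multiplying by *D* converts it to mEq.

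| Case | SD of share difference | 95% range of share | 95% shift (mEq) | Shift ÷ 17 |
|---|---|---|---|---|
| 10%, +20 | 0.060 | ±0.118 | ±2.4 | 14% |
| 15%, +30 | 0.071 | ±0.140 | ±4.2 | 25% |
| 25%, +40 | 0.087 | ±0.170 | ±6.8 | 40% |

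**Step 2. Power of the unadjusted t-test.** Leaving the factor out raises the variance from 30² = 900 to 900 + *p*(1 − *p*)*D*². Power for 17 mEq is from the noncentral t distribution with 98 degrees of freedom and noncentrality 17/(SD × √(2/50)).

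| Case | Added variance | Total SD | Variance ratio | Power |
|---|---|---|---|---|
| Fully accounted for | 0 | 30.0 | 1.00 | 0.80 |
| 10%, +20 | 36 | 30.6 | 1.04 | 0.79 |
| 15%, +30 | 114.75 | 31.9 | 1.13 | 0.75 |
| 25%, +40 | 300 | 34.6 | 1.33 | 0.68 |

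The variance ratio is also roughly the factor by which the sample would have to grow to restore power: about 13% more patients in the central case. Steps 1 and 2 describe the same cost in two ways and should not be added together.

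**Step 3. Could imbalance account for the whole pilot difference?** A shift of 17 mEq needs a share difference of 17/*D*.
- Central case: 17/30 = 0.567, about 28 more users in one arm, or 0.567/0.0714 = 7.9 SD. Only about 15 users are expected among all 100 patients.
- Upper case: 17/40 = 0.425, about 21 more users, or 0.425/0.0866 = 4.9 SD.

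Imbalance of that size is not a realistic possibility under these assumptions.

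**The case against.** **Randomisation already deals with this.** Largely true. Chance imbalance in any prognostic factor is part of the standard error of a two-group test, so the unadjusted comparison is unbiased over repeated randomisation and keeps its type I error. What remains is the lost precision and an uncorrected shift in the one trial that is run.

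**Imbalance could create or hide an effect of the pilot's size.** A reader might infer this from the open eligibility and the size of the arms. Nothing in the documents supports it, and step 3 shows that it would take an imbalance of 4.9 to 7.9 SD in the upper and central cases.

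**The information may be collected after all.** This stands in part. Section 9.0 paraphrases the question and does not show the form. The spreadsheet it refers to is not in the available text, and its medication and analgesic items might include home opioids. It would be too strong to say that preoperative opioid use will go unrecorded. The supported statement is that the plan does not specify its capture and does not use it in allocation or analysis.

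**All the size inputs are assumed.** Also true. At the low end (10%, +20 mEq) power drops by less than 2 percentage points. The case for acting rests on a likely strong predictor and a cheap remedy, not on a demonstrated large loss.

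**Broad enrolment is a legitimate choice.** Agreed. The point does not require a change to eligibility.

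**Conclusion.** The point holds as one of precision. Regular opioid users may enrol, the plan does not specify that their opioid use is recorded separately before surgery, and the primary comparison ignores it. Under the stated assumptions the chance shift has a 95% range of ±2.4 to ±6.8 mEq (14–40% of 17 mEq), and power falls from about 0.80 to between 0.79 and 0.68, with 0.75 in the central case. Prevalence, extra opioid need and SD are all assumptions, and the loss could be small.

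The documents do not support reading this as bias, as inflated type I error, or as a sufficient explanation for a difference of the pilot's size. The change is worth making because it costs little and the baseline definition has to be settled before enrolment.

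**What to change.** 1. **Section 9.0.** Replace the single question with two: (a) any opioid in the 24 hours before surgery, with drug and dose; (b) regular preoperative opioid use, yes or no, using one look-back window fixed before enrolment and checked against the Powerchart medication list. Record both before the injection is given.
2. **Section 11.0.** Prespecify the primary comparison adjusted for regular preoperative opioid use: a linear model of PACU morphine equivalents on arm plus this indicator, or a van Elteren (stratified Wilcoxon) test if the data are skewed. State the rule for choosing between them before unblinding.
3. **Optional.** The pharmacy could use separate blocked lists for users and non-users. With about 15 users expected in the central case, adjustment alone should recover most of the precision, and a block in the smaller stratum may stay incomplete.

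**Cost.** One reworded baseline question, a short chart check and slightly more analysis work. Consent is taken on the day of surgery (Section 22.0), so the chart check has to fit into that day; if lists are stratified, it must be done before the pharmacy order. No extra patients or visits are needed. The gain depends on the indicator being recorded accurately; misclassification would reduce it.

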7.0 Study Timelines

- Each individual subject who consents to the study will be participating from the day of their surgery until their two week postoperative appointment. Their coded data will remain in use until the study is complete, upon which all data will be destroyed electronically or physically.
- The duration of this study is anticipated to be 18 months for collection of 100 participants, 50 for the therapeutic group and 50 for the control group.

Prospective Assessment of Perioperative Intra-Articular Morphine Injection in Hip Arthroscopy on Postoperative Pain Management

- The estimated date of completion for primary analysis will be 18 months from the beginning of the study (October 2016).

8.0 Study Endpoints

The primary endpoint is patient narcotic consumption in the PACU after hip arthroscopy. Narcotic consumption will be measured by converting the patient's opioid consumption during their PACU recovery duration into morphine equivalents. This conversion is necessary to standardize different types of narcotics that can be administered in the PACU. We will also be determining the utility of IA morphine and clonidine in decreasing the patient reported pain in the PACU and during the first postoperative week, time until discharge from the PACU, and the quality of patient recovery using the QoR-15 survey.

9.0 Procedures Involved

100 patients will be consented for this study. 50 for the "control group" injection and 50 for the "therapeutic group" injection. For patients who are consented and enrolled in this study, prior to surgery, [name] will place a written order to the OR pharmacy for the randomized injection. Each order placed will be associated with a sequential study number (1-100) to keep track of each patient and the intervention that they received. The OR pharmacy will randomize the injection into the control or therapeutic group, so as to keep the team involved in patient care blinded to the intervention.

In the preoperative holding area prior to surgery, all patients will be asked to fill out the QoR-15 questionnaire (see Appendix), rate their current level of pain on the Visual Analog Scale (0-10), and be asked if they have taken any pain medication in the past 24 hours. Those in the control group will receive a 11 mL injection of .9% normal saline, and the therapeutic group will receive a 11 mL injection of 10 mg morphine and 100 mcg of clonidine in .9% NaCl solution. Both injections will occur at the conclusion of the hip arthroscopy procedure. All other pre, peri, and postoperative procedures will follow the standard of care.

Postoperatively, pain scores, amount of narcotics used, and discharge times, which are recorded in the patient's medical record as part of standard of care, will be collected. The control group will be compared to the therapeutic group. All postoperative pain management will follow the normal standard of care procedures for hip arthroscopy patients.

Additionally, patients will be sent home with a short "diary" for logging their pain and narcotic consumption in the first week following surgery. They will be rating their pain and logging narcotic consumption at 6, 18, 24, 48 hours, and 7 days postoperatively. This diary will be collected from the patient at their two week follow-up appointment.

The research procedures required for this protocol include the intra-articular injection at the conclusion of the hip arthroscopy procedure. At

Prospective Assessment of Perioperative Intra-Articular Morphine Injection in Hip Arthroscopy on Postoperative Pain Management

the conclusion of the hip arthroscopy, before closing the incision with sutures, an intra-articular injection of both morphine and clonidine, for the therapeutic group, or normal saline, for the control group, will be performed. All other operative procedures will occur as standard of care to ensure optimal patient safety.

- All standard of care procedures will take place for a hip arthroscopy procedure. No additional procedures are needed to reduce the magnitude of risk, as patients with a contraindication to morphine or clonidine will not be enrolled in the study, and patients will be under the watch of nurses, physician assistants, and doctors while in the postoperative recovery room.
- The only drugs used in this study that are beyond the standard of care for hip arthroscopy are intra-articular morphine and clonidine. In the context of this study, morphine and clonidine are FDA approved drugs for non-approved use. The control group will receive intra-articular normal saline, which is FDA approved.
- Northwestern's Powerchart electronic medical record system will be used to access patient medical records for those who consent to the study. Basic patient demographics, pre and post-op VAS pain scores, discharge times, and narcotic/analgesic consumption will be recorded from data in the medical records. The QoR-15 survey will also be used to assess patient quality of recovery. All data will be coded and stored in the attached Excel spreadsheet, which will be on a database in [name] locked office, only accessible to research personnel of the project via an encrypted password. All paper based documents will be kept in a locked cabinet in [name] office.

All data collected for this study can be found in the attached MS Excel spreadsheet and sample QoR-15 survey. Data points include age, sex, height, weight, tobacco use, VAS pain scores, discharge times, duration of surgery, discharge criteria score, medication use, and the following quality of recovery scores (as seen in the QoR-15): comfort, independence, and support. The postoperative diary will be asking patients for VAS pain scores, narcotic consumption, and potential complications at 6, 18, 24, 48 hours, and 7 days postoperative.

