11.0 Data and Specimen Management

All analyses will use the database with a coded study number as the patient indicator. The data will be analyzed with a Student's T-Test, non-parametric Mann Whitney test, and chi-square test.

All analyses will use the database with a coded study number as the patient indicator. Additionally, all information will be stored in a locked room on a password protected computer. As aforementioned, patient identifiers will be kept separately from medical data. Only the PI will have access to the patient identifier list, and only the PI and co-investigators will have access to the coded database. All non-electronic information, including consent forms, QoR-15 surveys, and patient postoperative diaries will be kept in a locked file cabinet in [name] office.

- The data extracted from the chart review will be maintained in a computer that is located in a secure area accessible only by research personnel of the project via an encrypted password. The computer is password protected and logs out the current user if no activity is detected for five minutes. The electronic data storing patient identifying information will be stored on a single password protected computer in [name] office in the Department of Orthopedics ([name]).
- Data will be stored until the completion of the study, whereupon all data with personally identifying health information will be destroyed. All paper based data will be placed in a locked bin to be destroyed by Citadel Management once the study is complete.

Prospective Assessment of Perioperative Intra-Articular Morphine Injection in Hip Arthroscopy on Postoperative Pain Management

- Only the PI will have access to the patient identifier list, and only the PI and co-investigators will have access to the database for analysis.
- The PI and co-investigators will be the only ones handling data.
- The patient identifier list will never leave the password protected computer in [name] locked office. Any electronic transmission of the coded data will occur over Northwestern's secure Microsoft Outlook email service and will only be accessed through Northwestern's secure remote database, FSMFiles.

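### The QoR-15 is scheduled only before surgery, so the quality-of-recovery endpoint in section 8.0 has no stated postoperative measurement

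*Combined protocol and SAP*

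**What the plan says.** Section 8.0 names PACU narcotic consumption as the primary endpoint. It then lists pain, time to PACU discharge and "the quality of patient recovery using the QoR-15 survey" as further effects to be determined. Pain is tied there to the PACU and the first postoperative week; the QoR-15 is given no time.

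Section 9.0 sets the one timed administration: "In the preoperative holding area prior to surgery, all patients will be asked to fill out the QoR-15 questionnaire". The same section places both injections at the end of the procedure. What it lists for collection after surgery is pain scores, narcotic use and discharge times from the chart, plus a take-home diary. The diary's content is given as: "The postoperative diary will be asking patients for VAS pain scores, narcotic consumption, and potential complications at 6, 18, 24, 48 hours", and also at 7 days. It is handed in at the two-week appointment.

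Section 9.0 also says that the survey serves to assess quality of recovery, and it lists among the data points "the following quality of recovery scores (as seen in the QoR-15): comfort, independence, and support". For full detail it refers to attachments: "All data collected for this study can be found in the attached MS Excel spreadsheet and sample QoR-15 survey".

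Section 11.0 treats the surveys and the diaries as separate papers: "All non-electronic information, including consent forms, QoR-15 surveys, and patient postoperative diaries will be kept in a locked file cabinet". The whole analysis statement is: "The data will be analyzed with a Student's T-Test, non-parametric Mann Whitney test, and chi-square test".

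**The concern.** An endpoint meant to show an effect of treatment has to be measured after treatment. The only QoR-15 with a stated time is completed before the patient enters the operating room. If staff collect only what section 9.0 schedules, the trial ends with 100 baseline scores and no outcome scores, and one of the four effects named in section 8.0 cannot be evaluated. A recovery score missed at its time cannot be recovered later.

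If staff instead assume that a postoperative form is wanted, each may choose a different moment. PACU discharge, any diary time and the two-week visit all lie within the participation period in section 7.0. Scores from different stages of recovery would then be pooled, and the time point to report could be chosen after the data are seen. The unnamed score adds to this: the survey as a whole and three separate scores are all mentioned, and none is designated for the comparison.

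**Working it through.** The plan gives no figure to reproduce on this point. The main check is a reading of every mention of the QoR-15 and every postoperative collection list.

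**Mentions of the QoR-15**

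| Section | Content | Time given |
|---|---|---|
| 8.0 | Listed as a non-primary effect | None |
| 9.0, preoperative paragraph | Form completed in the holding area | Before surgery |
| 9.0, record and data list | Purpose of the survey; comfort, independence and support scores | None |
| 10.0 | Storage of surveys | None |
| 11.0 | Storage of surveys, listed apart from diaries | None |
| 25.0 | Privacy of survey answers | None |

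**Postoperative collection routes**

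| Route | Items listed | QoR-15 listed |
|---|---|---|
| Chart (9.0) | Pain scores, narcotics, discharge times | No |
| Diary, procedures text (9.0) | Pain, narcotics at 6, 18, 24, 48 hours and 7 days | No |
| Diary, data list (9.0) | VAS, narcotics, complications at the same times | No |
| Two-week visit (9.0) | Collection of the diary | No |

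Result: 1 preoperative administration and 0 stated postoperative administrations, against 5 timed diary entries. The injection comes at the end of the operation, so the single timed form precedes treatment in both arms.

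**What the existing baseline could add**

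This part sizes the optional adjustment in the fix, not the defect.

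- Inputs from the plan: 50 per arm (sections 7.0, 9.0 and 23.0) and an unadjusted two-sample test (section 11.0).
- Assumed: two-sided 5% level, 80% power, and correlation r between preoperative and postoperative scores. The documents give none of these.

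Unadjusted detectable difference, in SD units: the normal approximation is (1.960 + 0.842) × √(2/50) = 2.802 × 0.200 = 0.560. The t-test on 98 degrees of freedom gives 0.566.

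With the preoperative score as covariate, the detectable difference is multiplied by √(1 − r²):

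| r (assumed) | 1 − r² | Detectable difference, 50 per arm |
|---|---|---|
| 0.3 | 0.91 | 0.566 × 0.954 = 0.540 SD |
| 0.5 | 0.75 | 0.566 × 0.866 = 0.490 SD |
| 0.6 | 0.64 | 0.566 × 0.800 = 0.453 SD |

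If only 40 per arm returned the form (also assumed), the unadjusted figure is 0.634 SD. The adjusted range is 0.634 × 0.954 = 0.605 SD down to 0.634 × 0.800 = 0.507 SD.

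**The case against.** The strongest reply is that the schedule may exist where we cannot see it. Section 9.0 refers to an attached spreadsheet, a sample survey and an Appendix, and a data-collection spreadsheet is a natural place for pre- and postoperative QoR-15 columns. This stands as a limit: the secure claim is that the protocol text gives no postoperative time. It does not remove the need for a change. Section 20.0 says the printed protocol will be each team member's reference, so its text should carry the schedule.

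A second reply is that postoperative use is plainly intended, because section 9.0 says the survey serves to assess recovery. That is accepted. But intent supplies no time, mode or collection route. Separate storage of surveys and diaries in section 11.0 is only weak evidence that the diary does not carry the form; the two diary descriptions, which omit it, are the stronger evidence.

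Third, with randomised allocation and a blinded care team, uneven timing would mainly add noise rather than bias between arms. That is fair. That recovery scores vary with time since surgery is also our assumption, although a reasonable one. Neither point helps if no postoperative form is collected.

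Finally, ANCOVA is not needed to close the gap, and the detectable differences do not measure its harm. Both points are right. The tests in section 11.0 would be valid on a postoperative score; they would simply leave unused a baseline that the plan already collects.

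**Conclusion.** The concern holds. As the text stands, the QoR-15 is timed once before treatment and never after it, and the score to be compared is not named. The quality-of-recovery endpoint therefore cannot be evaluated from the scheduled assessments. This rests on the protocol text alone; a schedule in the spreadsheet or Appendix would reduce the matter to copying it across.

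The reach is limited. The QoR-15 is not the primary endpoint and is not among the three measures in section 1.0. PACU opioid use, VAS pain and PACU time are unaffected. The point should be corrected but does not threaten the main result. The precision gain is secondary and depends on the assumed r.

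**What to change.** - **Section 9.0:** add the QoR-15 to the take-home diary at one named existing diary time, for example 24 hours, to be returned with the diary at the two-week visit.
- **Section 8.0:** define the endpoint as the postoperative score at that time. State whether this is the total or the comfort, independence and support scores; if the three scores, name one as the main comparison.
- **Section 11.0:** compare arms by ANCOVA with the matching preoperative score as covariate. A t-test or Mann-Whitney test on the postoperative score would be an acceptable but less precise alternative.
- **If the spreadsheet or Appendix already sets a postoperative time:** copy it into sections 8.0 and 9.0.
- **If no postoperative form is intended:** remove the endpoint from section 8.0.

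The cost is one more diary page, slight added patient burden, some risk of unreturned forms, and a minor amendment. Removing the endpoint costs only the amendment. Adjusting for the baseline needs no new data beyond the postoperative form.
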